**The overarching hypothesis of this proposal is that aberrant brain responses to visceral pain signals within the homeostatic afferent processing network (HAPN) represent the primary mechanism responsible for bowel pain experiences in a subset of IBS patients (IBS-HAPN).** Our preliminary data has identified a pattern of brain activation differences within the HAPN following visceral stimulation in IBS subjects compared to healthy controls. Using fMRI, I will further characterize the HAPN pain responses of IBS-S subjects to additional non-visceral stimuli and following antidepressant therapy. I predict that this protocol will reveal a pattern of increased HAPN pain activations to both visceral and somatic stimuli—activations that are refractory to antidepressant pharmacotherapy. Ultimately these findings will demonstrate the mechanistic importance of the HAPN to pain experiences in the IBS-S subgroup.

*These goals will be realized through the pursuit of the following Specific Aims:*

**Specific Aim 1. To compare HAPN activations following noxious somatic stimulation in IBS subjects based on the presence of somatization.**

*Hypothesis 1:* As a result of a generalized abnormal pain response within the HAPN, IBS-S subjects will demonstrate greater HAPN activations with noxious somatic stimuli, compared to IBS subjects with no somatization and healthy controls.

**Specific Aim 2. To compare the effects of antidepressant therapy HAPN activations following noxious visceral stimulation in IBS subjects based on the presence of somatization.**

*Hypothesis 2:* Consistent with clinical refractoriness to antidepressant treatment, IBS-S subjects will demonstrate a persistent pattern of abnormal HAPN visceral activations following desipramine therapy, whereas significant improvements in HAPN visceral activations will be observed in IBS subjects with no somatization following antidepressant therapy.

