**Specific Aim 2. To compare the effects of antidepressant therapy HAPN activations following noxious visceral stimulation in IBS subjects based on the presence of somatization.**

Rationale: Case-control and randomized clinical trial data have established that somatization predicts symptom responses to IBS therapy with the tricyclic antidepressant desipramine. Specifically, IBS-S subjects are more refractory to antidepressant therapies, while IBS-No S subjects have better overall responses to the same treatment. A recent study has demonstrated improvements in HAPN visceral activations (anterior cingulate cortex) following desipramine therapy in an IBS cohort. Given these observations, the goal of this Aim is to assess whether differences in visceral HAPN activation patterns following desipramine treatment can be detected in IBS-S and IBS-No S subjects.

Design and Methods: The proposed study implements open-label desipramine therapy in 40 IBS (20 IBS-S and 20 age-matched IBS-No S) subjects. Participants from Aim 1 will be invited to continue on to open-label therapy in Aim 2. IBS-S and IBS-No S subjects will receive a 4-week treatment course with the tricyclic antidepressant desipramine (DES), as detailed in section 2.D., below. Subjects will undergo a fMRI protocol with noxious visceral and somatic stimuli as in Aim 1 at baseline, and then immediately following the 4-week desipramine therapy. Subjects will undergo baseline, and post-therapy assessment of psychiatric comorbidity (depression/anxiety) and IBS symptom severity (as described in 3.A. and 3.B., below). The primary endpoint is differences in visceral stimulation-induced brain activations of the HAPN on fMRI, ascertained between-groups following desipramine therapy. The proposed study design is outlined in Figure 9.

[figure not shown]
**Figure 9. Overview of study design for Specific Aim 2.** IBS patients with somatization (IBS-S) and without somatization (IBS-No S) will be identified. A baseline fMRI protocol (as in Aim 1) will be obtained at baseline, followed by a 4-week, open-label treatment with desipramine. A second fMRI protocol will be performed post-desipramine therapy at week 4. The primary endpoint of interest is post-treatment differences in visceral HAPN activations between IBS-S and IBS-No S subjects.

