Analysis/interpretation: *Consistent with the clinical refractoriness to antidepressant therapy observed in IBS-S subjects, it is hypothesized that IBS-S subjects will exhibit a persistent pattern of abnormal HAPN activations in response to visceral stimulation following desipramine therapy.* By comparison, it is hypothesized that the IBS-No S group will exhibit decreases in HAPN activations in the post-treatment fMRI protocol (Figure 10, below). Region of interest two-way ANOVA models will be developed in comparing  $\Delta$ baseline-DES activations, with IBS Group (IBS-S and IBS-No S) as a between-subject factor. If the stated hypothesis is supported by the fMRI findings, it would suggest that the persistent HAPN activations in response to visceral afferent signals may result in the less robust clinical responses to desipramine therapy in the IBS-S. This finding would be an important addition to the existing literature, providing both insight into the central mechanisms involved in IBS antidepressant response, and also into the specific relevance of HAPN pain responses to the IBS-S subgroup.

Conversely, should HAPN activations be found to improve in both IBS groups following desipramine therapy, the possibility that HAPN visceral activations are indeed partially refractory to desipramine in IBS-S, but the detected between-group differences (IBS-S vs. IBS-No S) in post-desipramine changes in HAPN activation were smaller than expected, and thus not statistically significant. If this were the case, the ANOVA analyses would be likely demonstrate statistical trends between the IBS groups, and enrollment of additional subjects would be considered if feasible following power calculations. This additional step might lead to findings which allow for rejection of the null hypothesis.

[figure not shown]

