**Pitfalls/Limitations:** Pitfalls and limitations as described in Aim 1 are also applicable to this Aim, and will be addressed as outlined previously. Also a consideration is the use of repeated fMRI measures within the same individual, and the influence that previous experiences will have on subsequent fMRI studies (e.g., anticipation). Theoretically this effect should be distributed across treatments and IBS study groups equally, such that the anticipated effect, if any, bias towards the null. Existing literature discussing this phenomenon suggests that the proposed regionwise analyses based in *a priori* hypotheses are more immune to this phenomenon. This study is proposed without a placebo control arm. This design was decided upon after discussion with my mentors in order to facilitate subject recruitment and protocol adherence. While an obvious limitation of the study design, given previous data that demonstrates the effects of tricyclic medications over placebo within the HAPN, foregoing a placebo-controlled arm was felt to be a reasonable approach.

The observed changes HAPN activation seen following desipramine therapy in this Aim likely represent the direct effects of desipramine on these brain regions. This conclusion can be deduced from previous pharmacoradiologic and animal model studies demonstrating the actions of tricyclic antidepressants in these regions. The possibility remains, however, the desipramine is influencing the CNS proximal to the HAPN (i.e., at the level of the viscera, spinal cord, or brainstem), in turn decreasing HAPN activations via a reduction in visceral afferent signals. This possibility can be reconciled in future analyses which examine the data generated by this Aim, utilizing sophisticated functional connectivity models to establish the temporal relationships of these regional activations.

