**Figure 10. Summary of the anticipated findings in Specific Aims.** It is hypothesized that IBS-S subjects will demonstrate greater HAPN activations with noxious somatic stimuli, compared to IBS subjects with no somatization (IBS-S) and healthy controls (Specific Aim 1). It is also anticipated that IBS-S subjects will demonstrate a persistent pattern of abnormal HAPN visceral activations following desipramine therapy, whereas significant improvements in HAPN visceral activations will be observed in IBS subjects with no somatization following antidepressant therapy (Specific Aim 2). n/a=not assessed--control subjects do not participate in treatment arm of Specific Aim 2.

This study is proposed without a placebo control arm. This design was decided upon after discussion with my mentors in order to facilitate subject recruitment and protocol adherence. While an obvious limitation of the study design, given previous data that demonstrates the effects of tricyclic medications over placebo within the HAPN, foregoing a placebo-controlled arm was felt to be a reasonable approach.

**Future directions.** Recent epidemiologic studies have demonstrated greater prevalence of functional genetic polymorphisms of monoaminergic neurotransmission, including the serotonin transport protein (SERT), in IBS compared to healthy controls. Neurophysiologic studies in animal models and mood disorders have identified serotonin as important to nerve signaling within the HAPN. In future studies, I will attempt to link established serotonergic genetic polymorphisms (such as SERT) to the presence of CNS activation patterns in IBS subjects. Studies to-date evaluating the genetic basis of IBS have evaluated IBS subjects as a single group. The presumed heterogeneity in IBS pathophysiology has driven the need for large samples of several hundred individuals to ascertain even weak

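### Aim 2 cannot claim that repeat-scan effects bias toward the null: with one open-label drug and a fixed scan order, scan order and desipramine are confounded within each group

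*Combined protocol and SAP*

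**What the plan says.** The Pitfalls/Limitations text of Specific Aim 2 raises the influence of earlier scans on later ones, with anticipation as its example, and disposes of it thus: "Theoretically this effect should be distributed across treatments and IBS study groups equally, such that the anticipated effect, if any, bias towards the null". It adds that the literature suggests regionwise analyses based on prior hypotheses are less affected.

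The design is set out under the same Aim and in the captions of Figures 9 and 10:

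- One treatment: "The proposed study implements open-label desipramine therapy in 40 IBS (20 IBS-S and 20 age-matched IBS-No S) subjects".
- Fixed order, with a baseline scan first: "A second fMRI protocol will be performed post-desipramine therapy at week 4".
- No placebo: "This study is proposed without a placebo control arm". The plan calls this an obvious limitation and gives recruitment and adherence as the reasons.
- No rescanned healthy controls: "n/a=not assessed--control subjects do not participate in treatment arm of Specific Aim 2".

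Hypothesis 2 has two halves. Abnormal activation persists in IBS-S, "whereas significant improvements in HAPN visceral activations will be observed in IBS subjects with no somatization following antidepressant therapy". The Aim 2 Analysis/interpretation text repeats the second half: "it is hypothesized that the IBS-No S group will exhibit decreases in HAPN activations in the post-treatment fMRI protocol". The model given there is an ANOVA of the baseline-to-desipramine change with IBS group as the between-subject factor. The Figure 9 caption words the primary endpoint instead as a post-treatment difference between the groups.

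On cause, the Pitfalls/Limitations text states: "The observed changes HAPN activation seen following desipramine therapy in this Aim likely represent the direct effects of desipramine on these brain regions". The only alternative it considers is desipramine acting at another level, such as the gut, spinal cord or brainstem.

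**The concern.** Balance across treatments needs at least two treatments. Here every rescanned subject has taken desipramine and every second scan follows it. Within a group, the change from scan 1 to scan 2 is the sum of any drug effect and any repeat-scan effect, and nothing in the design tells them apart.

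This matters because half of Hypothesis 2 is a within-group fall. If subjects respond less to a second distension session for reasons unrelated to the drug, that half is favoured, while the text tells the reader that the bias runs the other way. The plan then attributes observed change to the drug and names no non-drug cause. The same gap appears in the Analysis/interpretation text. If both groups improve, which an equal downward repeat-scan effect would produce, the plan raises partial refractoriness in IBS-S and possible further enrolment, but not repeat scanning.

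**Working it through.** **Logic.** Let D be the drug effect and R the repeat-scan effect on visceral activation, with subscripts S and N for IBS-S and IBS-No S.

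- Within-group change, IBS-No S: D_N + R_N. If D_N = 0, the expected change is R_N. A negative R_N moves the test away from the null, in the predicted direction. A positive R_N opposes and can hide a real fall.
- Between-group difference in change: (D_N − D_S) + (R_N − R_S). If R_N = R_S the second term is zero, so there is no bias in either direction. If they differ, the sign of the bias is the sign of R_N − R_S.

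So the plan's statement is wrong for the within-group change. For the between-group contrast, the accurate statement is no bias if R_N = R_S. Equality is asserted without evidence.

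**Size.** The plan gives no figure for this effect, so there is none to reproduce. Inputs:

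- Completers: 20 − 2 = 18 per group, from the 10% attrition in the sample size section.
- True drug effect zero, two-sided alpha 0.05 (assumed).
- Repeat-scan fall h = 0.33 or 0.5 SD of a single-scan response (assumed). The 0.33 in the sample size section is a treatment effect of unstated metric and is no evidence for h.
- Scan-rescan correlation ρ = 0.5 or 0.7 (assumed).

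The SD of change in single-scan SD units is √(2(1−ρ)), which is 1.000 at ρ = 0.5 and 0.775 at ρ = 0.7. The standardised change is dz = h/√(2(1−ρ)).

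Paired test in IBS-No S: noncentral t, 17 df, noncentrality dz√18, critical value 2.110. Between-group test of change when only IBS-No S shifts: noncentral t, 34 df, noncentrality dz√(18/2) = 3dz, critical value 2.032. If both groups shift equally, separate paired tests give a significant fall in IBS-No S and none in IBS-S with probability p(1−p), where p is the paired-test probability.

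| h | ρ | dz | paired noncentrality | p: IBS-No S fall significant | p(1−p), equal shift | between-group test, only IBS-No S shifts |
|---|---|---|---|---|---|---|
| 0.33 | 0.5 | 0.330 | 1.400 | 26% | 19% | 16% |
| 0.33 | 0.7 | 0.426 | 1.807 | 40% | 24% | 24% |
| 0.5 | 0.5 | 0.500 | 2.121 | 52% | 25% | 31% |
| 0.5 | 0.7 | 0.645 | 2.739 | 73% | 20% | 47% |

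The nominal rate for a significant fall in one group is 2.5%. With equal shifts, a simulation of 100,000 trials (18 per group, shifts of 0.2 to 0.8 SD of the change score) kept the between-group test at 5.0-5.1%. The same simulation gave 19% at 0.33 and 25% at 0.5 for the split result from separate tests, matching the table's ρ = 0.5 rows.

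**The case against.** The strongest reply is that the quoted sentence names IBS groups as well as treatments, and the group half protects what the plan tests. The primary endpoint and the only specified Aim 2 model are between-group, and an equal shift leaves that test at its nominal level. This stands. It supports a claim of no bias if the groups shift equally, but not a claim of bias toward the null.

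A reader might go further and infer that habituation alone would reproduce the full predicted pattern, or that the primary contrast is biased toward the hypothesis. The documents support neither. An equal fall would also lower IBS-S, against the predicted persistence. The pattern needs unequal shifts or a reading of two separate within-group tests, and nothing in the documents shows that IBS-S habituate less. The direction is open too: anticipation, the plan's own example, could raise the second response.

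Equality still cannot be presumed. Mean Beck Anxiety scores in the preliminary study were 19.9 in IBS-S and 3.1 in IBS-No S. The exclusion of anxiety disorder may narrow that gap, but the plan does not show that it closes it.

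Three further replies have some force. The missing placebo arm is disclosed, though never linked to repeat scanning. Cited evidence of tricyclic effects over placebo makes a drug effect plausible, but does not separate it from scan order here. The paired IBS-No S test is not specified as a model: it is inferred from the wording of Hypothesis 2, and the table does not apply the planned small volume correction. The claim that regionwise analyses are less affected cannot be checked from the documents.

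**Conclusion.** The point holds for the bias statement and for the causal attribution. In a one-treatment, fixed-order design without a rescanned comparator, within-group change cannot be credited to desipramine, and a repeat-scan effect on it need not run toward the null. Under the assumed inputs, a repeat-scan fall of 0.33-0.5 SD makes the IBS-No S fall significant 26-73% of the time with no drug effect. Separate tests then show a fall in IBS-No S only about 19-25% of the time, even when both groups shift equally.

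The between-group difference in change is sound if the shift is equal (about 5%) and at risk only if it is not. The 16-47% range is the extreme case in which one group shifts and the other does not. The logic needs no assumed sizes. The percentages do, and they are illustrations rather than estimates for this trial.

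**What to change.** 1. In Aim 2 Pitfalls/Limitations, replace the bias sentence. State that within each group repeat-scan effects are confounded with desipramine and may inflate or mask a fall. State also that the between-group difference in change is unbiased if the effect is equal and additive, and may be biased either way if it is not.
2. Withdraw the conclusion that observed changes likely reflect direct desipramine effects.
3. State that Hypothesis 2 is judged only by the between-group difference in change (Group x Time, the change-score ANOVA already planned), and reword the post-treatment-difference endpoint to match.
4. Report within-group changes as descriptive and not attributable to the drug. Do not infer refractoriness from a significant fall in one group and a non-significant one in the other.
5. In Analysis/interpretation, add a repeat-scan effect to the explanations if both groups improve.
6. Changes in the planned control regions and in somatic responses may be shown by group as description only. The control regions are chosen because they are not expected to differ between the populations, and somatic responses at week 4 are also measured after treatment, so neither can separate drug from repeat scanning.

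The cost is wording and a narrower conclusion, with no new arm, visit or subject. These changes do not remove the confounding. Separating drug from scan order would need a rescanned untreated comparator, which this design lacks.

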## 2. Source of subjects/calculation of estimated subject pool.

**A. Irritable bowel syndrome and somatization.** Based on published reports, it is conservatively estimated that approximately 15% of the US population is affected by irritable bowel syndrome. It has been observed by our group and others that somatization is present in 25-42% of IBS patients. Similarly, we have previously identified that within our gastroenterology referral clinic population that approximately 30% of IBS patients have no somatization features (IBS-No S).

**B. Subject pool.** Patients undergoing evaluation for, or presently under medical management for, a diagnosis of IBS at the Washington University Gastroenterology clinic by from the period of Jan 2009 until the completion of the study enrollment period, if interested, will be assessed for participation eligibility. Given my clinical focus on IBS and related functional GI disorders, it is estimated that approximately two-thirds of the patients seen in my

outpatient office meet criteria for IBS. I see an estimated 400 new patients a year in the office, of whom around 260 would be expected to have IBS. Primary recruitment efforts for the study population thus will be based in this setting. This strategy was successful in recruiting subjects to generate the primary data for this proposal.

**C. Screening, eligibility, and patient enrollment.** IBS subjects with- and without somatization features will be recruited. To be eligible, subjects will have to be between 18 and 90 years of age (inclusive) and qualify for a diagnosis of irritable bowel syndrome according to the criteria set forth in the Rome III criteria. Comorbid somatization in these IBS subjects will be determined using the Patient Health Questionnaire-15 (PHQ-15). Only subjects with high somatization (PHQ-15  $\geq 10$ ), or low somatization (PHQ-15  $\leq 5$ ), excluding GI symptoms, will be considered for enrollment. Medical history and chart review will be used corroborate the PHQ-15 score, requiring that IBS-S subject  $\geq 2$  additional somatization syndromes, while IBS-No S subjects have a history of  $\leq 1$  non-GI somatization syndrome. Persons are eligible to participate without regard to race or ethnicity. Given sex differences in cerebral responses to noxious stimuli and the greater prevalence of IBS in women, only female participants will be sought in this study. In view of brain hemispheric differences between left- and right-hand dominant individuals, all participants must be right-handed.

*Persons are excluded from participation for having various psychiatric, medical, and other characteristics.*

Psychiatric/cognitive exclusions include any of the following: active suicidal or homicidal ideation or a history of attempted suicide, current excessive alcohol use or other substance abuse disorders, active major depression, anxiety disorder, bipolar depression or any psychotic disorder, unwillingness to be randomized or provide informed consent, inability to communicate with staff or significant cognitive impairment.

Medical and other exclusions include any of the following: renal or hepatic disease or impairment, diabetes, cardiovascular disease, cardiac arrhythmia, cerebrovascular disease, or breastfeeding, pregnant, or imminent intention of pregnancy, history of seizures or primary neurological disorder, head trauma, brain damage, hyper- or hypothyroidism, history or abdominal surgery (other than cholecystectomy/appendectomy), or known structural GI disorder (Crohn's disease, etc.), contraindication to MRI (metallic implant, pacemaker), or rectal balloon distention (e.g., proctitis/colitis).

Exclusions related to medications: 1. Analgesics (narcotics, NSAIDs; acetaminophen OK), 2. Muscle relaxants 3. Psychoactive agents (antidepressants, antipsychotics) 4. Other medications (phenytoin; amphetamines, prescription weight-loss drugs, or benzodiazepines); 5. Thyroid medication; 6. Anticholinergic medications or other IBS medications (hyoscyamine, dicyclomine), 7. Cytochrome p450 substrates, 8. Participation in any clinical trial using any other drug.

**D. Desipramine therapy (Aim 2).** Aim 2 utilizes desipramine, a standard-of-care option in the clinical management of IBS. Desipramine is a tricyclic antidepressant that has considerable clinical experience, and controlled-trial evidence supporting its use in the management of IBS symptoms. *Dosing of desipramine is as follows:* Starting dose: Desipramine 25 mg/day administered in the evening. Dosing may be increased dependent upon side-effects and clinical response to a maximum of 100 mg/day. Absent significant side-effects, all patients are increased at the one week visit to 50 mg/day at bedtime if they have not achieved a report of "Adequate relief" (Assessment measures, B.3., below). Thereafter, up to week 4, the daily desipramine dose may be increased weekly by 25 mg up to the 100 mg/d maximum. All doses will be dispensed by the Barnes-Jewish Hospital (BJH) study pharmacy, and supervised by the investigator.

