### 2. Somatization is an important clinical feature in IBS, and portends greater IBS morbidity.

Somatization is a condition defined by the expression of pain syndromes across multiple organ systems (bowel, musculoskeletal, etc.) in the absence of any identifiable physical abnormality to explain the reported pain. It is likely that the multiple pain symptoms associated with somatization are the result of a common abnormal CNS interpretation of peripheral pain signals, rather than a simultaneous sensory malfunction of several organ systems. We and others have found that 25-42% of IBS subjects attending gastroenterology referral clinics have identifiable somatization with standard instruments (PHS-15) and medical history. Clinically, the presence of somatization in IBS patients (IBS-S) bears prognostic importance: compared to IBS patients without somatization (IBS-No S), IBS-S subjects report significantly greater numbers of: a) GI and non-GI symptoms, b) missed work days, and c) urgent care visits and physician consultations. Recently we demonstrated somatization in IBS predicts both more intense abdominal pain experiences, and poor bowel symptom responses to centrally-active pharmacotherapies (e.g., tricyclic antidepressants). We found that IBS-S subjects were 4.7 times more likely to report unsatisfactory treatment responses using antidepressant therapy, resulting in premature medication discontinuation (Figure 2).

**Figure 2. The importance of somatization to antidepressant treatment discontinuation in IBS subjects.** IBS subjects with greater somatization using two different somatization measures (somatization state and trait) were significantly more likely to experience premature antidepressant treatment discontinuation due to inefficacy and side-effect experiences. From Sayuk G, et al.

[figure not shown]
**Figure 1. The biological heterogeneity of irritable bowel syndrome (IBS).** Several unique mechanisms have been proposed as relevant to IBS pathophysiology. However, no single mechanism has been sufficient to explain IBS symptoms in all patients. Given that IBS is a symptom-based diagnosis, it is likely the result of a multiple of underlying mechanisms, emphasizing the importance of identifying pathophysiologically relevant IBS subgroups.

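### Desipramine dose is titrated on relief and side-effects, which are expected to differ by group, but the Aim 2 analysis and interpretation take no account of exposure; the direction of any resulting bias is unknown

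*Combined protocol and SAP*

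**What the plan says.** Section 2.D (Desipramine therapy) starts everyone at the same dose: "Starting dose: Desipramine 25 mg/day administered in the evening". After that the dose is individual. The general rule is "Dosing may be increased dependent upon side-effects and clinical response to a maximum of 100 mg/day". The week-1 step has two conditions, tolerability and lack of adequate relief: "Absent significant side-effects, all patients are increased at the one week visit to 50 mg/day at bedtime if they have not achieved a report". Later steps are optional: "Thereafter, up to week 4, the daily desipramine dose may be increased weekly by 25 mg up to the 100 mg/d maximum". The second scan is taken "immediately following the 4-week desipramine therapy" (Specific Aim 2, Design and Methods).

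The plan expects both titration drivers to differ by group. The Aim 2 rationale describes IBS-S as more refractory to antidepressants and IBS-No S as better responders. Background section B.2 gives a 4.7-fold higher likelihood of unsatisfactory response in IBS-S. The Figure 2 caption says that subjects with greater somatization "were significantly more likely to experience premature antidepressant treatment discontinuation due to inefficacy and side-effect experiences".

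The Aim 2 analysis compares the baseline-to-desipramine change in activation "with IBS Group (IBS-S and IBS-No S) as a between-subject factor". The sample size section also describes a single between-subjects factor, Group. The extra ANOVA models described under Aim 1, which the Aim 2 pitfalls carry over, cover disease duration, symptom severity and psychological features. The Aim 2 limitations discuss repeat scanning, the absence of placebo and the site of drug action. Dose appears in none of these places. Self-reported compliance is collected (section 3, GISQ Part D), but no analysis uses it.

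**The concern.** Aim 2 asks whether HAPN activation in IBS-S persists despite desipramine, and persistence would be read as a mechanism for the weaker clinical response. That reading needs the two groups to have had comparable drug exposure. Under the titration rule, exposure is itself an outcome of relief and tolerability, and the plan's own premises tie both to the grouping variable.

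There is no placebo or fixed-dose arm, so the design cannot separate less drug from less brain response to the same drug. Both possible errors matter. Lower exposure in IBS-S could look like refractoriness. Higher exposure in IBS-S could bring its activation down and hide refractoriness; for a result short of significance, the Aim 2 interpretation contemplates enrolling more subjects.

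**Working it through.** **The plan's own figure.** The plan gives no figure for exposure. The nearest is power of 0.82 for Group x Treatment with 20 per group and effect size 0.33. Taking 0.33 as Cohen's f, two-sided alpha 0.05 and zero correlation between the two scans (all assumed, since none is stated), the noncentrality is 0.33² x 80 = 8.71 on 1 and 38 df, and power is 0.820. With 18 per group, after the stated 10% attrition, it is 0.33² x 72 = 7.84 on 1 and 34 df, and power is 0.776. Nothing in this calculation allows for unequal exposure.

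**Range of exposure.** The permitted doses at the scan are 25, 50, 75 and 100 mg/day, so the range is 100/25 = 4-fold. For cumulative dose, assume increases at weeks 1, 2 and 3, full adherence and 28 days of treatment:

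| Weekly schedule (mg/day) | Cumulative (mg) | Mean (mg/day) |
|---|---|---|
| 25, 25, 25, 25 | 7 x 100 = 700 | 25 |
| 25, 50, 50, 50 | 7 x 175 = 1225 | 43.75 |
| 25, 50, 75, 75 | 7 x 225 = 1575 | 56.25 |
| 25, 50, 75, 100 | 7 x 250 = 1750 | 62.5 |

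The cumulative range is 1750/700 = 2.5-fold. In the last schedule the final dose has been taken for only one week at the scan.

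**Direction.** The two drivers, set side by side:

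- *Side-effects.* More side-effects in IBS-S would hold dose down or delay it.
- *Relief.* Less relief in IBS-S would trigger increases, while an IBS-No S subject with early relief may stay at 25 mg/day.

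The documents give no rate for either route on the dose scale, so the net imbalance cannot be derived.

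**Size if IBS-S exposure is lower (illustration).** Assume equal brain sensitivity, effect proportional to mean dose, and a full-schedule effect D in IBS-No S of 0.66 SD of the change score (2 x 0.33). With exposure ratio r (IBS-S over IBS-No S), the spurious difference is D x (1 - r). The chance of significance comes from the noncentral t with noncentrality D(1 - r) x √(n/2):

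| r | Spurious difference, D = 0.66 | Chance of p<0.05, n = 18 to 20 | Same, D = 1.0 |
|---|---|---|---|
| 0.8 | 0.13 SD | about 7% | about 9% |
| 0.6 | 0.26 SD | 12-13% | 21-23% |
| 0.4 | 0.40 SD | 21-23% | 42-46% |

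The last row is the extreme under these schedules: 25/62.5 = 0.4 would need every IBS-S subject held at the starting dose and every IBS-No S subject on the full schedule.

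**Size if IBS-S exposure is higher (illustration).** Suppose IBS-S sensitivity per mg is 0.7 of that in IBS-No S, IBS-S subjects average 62.5 mg/day and IBS-No S subjects 43.75 mg/day. Then 0.7 x 62.5 = 43.75 = 1.0 x 43.75. The two groups show the same change, and a 30% deficit in sensitivity disappears.

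**The case against.** The strongest objection concerns direction. A reader might infer that IBS-S subjects will be scanned on less drug, so that Aim 2 is biased towards declaring refractoriness. The documents do not support that. The most explicit dosing rule, at week 1, raises dose in those without relief, and the plan expects these to be mainly IBS-S subjects. The 4.7-fold figure concerns unsatisfactory response, which under section 2.D favours an increase. The Figure 2 evidence concerns stopping treatment, not a lower maintained dose; a subject who stops may simply miss the second scan, which is a question of attrition. All of this stands. The point is therefore that the direction is unknown, not that it favours the hypothesis.

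It can also be said that comparing groups after response-titrated therapy, which the plan describes as a standard-of-care option, is a legitimate question, and that the Aim 2 interpretation is worded cautiously. Both are fair. The group comparison can be run and is valid as a comparison of the two groups as treated. What it cannot do without exposure data is support the mechanistic step to HAPN refractoriness.

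Finally, adjusting for week-4 dose would not settle the matter. Dose is set after baseline by relief and tolerability, so the adjusted group contrast could be biased either way, and there are only 18 to 20 subjects per group. This stands too, and it limits what the fix may ask for.

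**Conclusion.** The concern holds in a form without direction. Dose depends on two outcomes that the plan expects to differ by group, Group is the only between-subject factor named in the Aim 2 model, and exposure is missing from both the additional models and the limitations. A difference between IBS-S and IBS-No S, or the absence of one, could partly reflect exposure.

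The 4-fold range in dose at the scan follows directly from section 2.D. The 2.5-fold cumulative range rests on assumed timing of the steps. The error rates rest on an assumed proportional dose-response, an assumed effect size and assumed exposure ratios; they show scale and do not predict the trial's error rate. This should be corrected because it changes what Aim 2 can conclude. It does not invalidate the primary comparison.

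**What to change.** Leave the dosing rule and the primary analysis as they are, and make three additions.

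1. Report by group: dose at the week-4 scan, cumulative dose, time at final dose, and adherence. The study pharmacy already dispenses every dose, and self-reported compliance is already collected.
2. State in the Aim 2 interpretation, before the data are analysed, that persistent IBS-S activation supports HAPN refractoriness only where IBS-S exposure is similar to or higher than IBS-No S exposure. If it is lower, report that exposure and refractoriness cannot be separated. If it is higher, note that true refractoriness may be masked. Say in advance what will count as similar.
3. A model with exposure as a covariate may be added as exploratory only, labelled as post-baseline and response-driven. It must not decide the conclusion.

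The cost is one extra table, a few sentences in the plan and a more qualified Aim 2 conclusion. No new data collection is needed beyond recording each dose change with its date.
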